5.2 Variables

Refer to **Annex 2: Variable definitions** for the definitions of all variables.

5.2.1.1 Patient characteristics

The following patient characteristics will be evaluated on each patient's cohort entry date:

- Age
- Sex
- Weight

For the entire cohort, a list of the top 10 non-HAE therapies used over the baseline period will also be evaluated. We will evaluate the most used therapeutic classes across all patients. In clinical practice, patients may be on additional therapies for comorbidities. Some of these therapies (e.g., estrogens) may be associated with increased risk of HAE attacks.⁴ We will provide descriptive information on the most common therapies outside of HAE treatment for patients within the cohort.

Note: weight values may be limited in the Clinformatics® Data Mart. If needed, we will create an additional HAE patient cohort in Optum's De-identified Integrated Claims-Clinical dataset, which combines adjudicated claims data with Optum's Electronic Health Record data, to obtain a larger sample of HAE patients with weight values.

5.2.1.2 Treatment

The main HAE treatments of interest are the prophylactic treatments reviewed in the prior ICER HAE report (see Annex 1 for more details):

- Takhzyro® (lanadelumab, Takeda Pharmaceutical Company, Ltd.)
- Haegarda® (C1 esterase inhibitor [human], CSL Behring, GmbH.)
- Cinryze® (C1 esterase inhibitor [human], Takeda Pharmaceutical Company, Ltd.)

Other on-demand therapies and prophylactic treatments will also be included. In instances where a generic is available, we will include both the brand and generic drug in the analysis.

- Berinert® (C1 esterase inhibitor [human], CSL Behring, GmbH)
- Firazyr® (icatibant, Takeda Pharmaceutical Company, Ltd.)
- Ruconest® (C1 esterase inhibitor [recombinant], Pharming Healthcare, Inc.)
- Kalbitor® (ecallantide, Takeda Pharmaceutical Company, Ltd.)
- Danazol
- Cyklokapron/Lysteda (tranexamic acid)
- Aminocaproic acid
- Oxandrolone
- Methyltestosterone
- Stanozolol

5.2.1.3 Outcome definitions

The following study outcomes are defined below.

5.2.1.4 HAE attack rates

Observational studies that evaluate attack rates in claims or EHR data sets are limited. There is currently no validated method to evaluate HAE attacks in claims data.

In creating our definitions of severe and non-severe attacks, we took guidance from clinical experts, treatment guidelines, and published literature that identified symptoms ([Longhurst & Bork 2019](#))⁵ or used diagnoses codes indicative of an attack (Tachdjian 2020).¹ Symptoms and diagnoses codes were cross referenced in a de novo code search to capture both ICD-9 and ICD-10 codes.

Attacks are defined by severity:

- **Severe attack:** Treatment guidelines and empirical data suggest that severe attacks are typically treated in the ED.⁶ For this analysis, severe attack will be defined in two ways: broadly as all-cause ED visits with or without hospitalization and more specifically as HAE ED visits with or without hospitalization. HAE specific severe attacks will be defined by a claim for an ED visit with or without hospitalization that includes diagnoses and drugs indicative of an attack (see Annex 2).
- **Non-severe attack-** Non-severe attacks are treated with on-demand therapy either by self-administration or administration by a healthcare professional. An attack treated by a healthcare professional will be defined as a medical service claim for an on-demand therapy occurring outside an inpatient or ED setting (e.g., physician office). For self-administration, we will estimate the number of attacks treated by calculating the number of doses dispensed based on dispensed quantity and approved dosages. Based on [treatment guidelines](#),⁶ patients should readily have on-demand therapy to treat two attacks, thus we will consider any doses dispensed over the two on-hand dosages of on-demand therapy as evidence of an attack.

Data on the duration of attacks by severity is limited, however attacks generally last between two and five days.⁷ Thus, on-demand therapy administrations by a healthcare professional, ED visits, and inpatient hospitalizations occurring within five days of each other will be considered part of a single attack. In cases where an on-demand therapy administration occurs within five days of an ED visit or hospitalization, the attack will be counted as a severe attack.

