5.2.1.8 Hospitalization utilization

For those patients with severe attacks, defined by inpatient hospitalization or ED visit, we will calculate the percentage of patients hospitalized. Of those hospitalized, we will also estimate utilization for the following:

- Percent of patients receiving cricothyrotomy/tracheotomy
 - Percent that also receive artificial respiration
- Percent of patients intubated
 - Percent that also receive artificial respiration

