5.3.1.2 General notes on administrative databases

Electronic outpatient pharmacy dispensing records are considered accurate because pharmacists fill prescriptions with little room for interpretation, and are reimbursed by insurers on the basis of detailed, complete, and accurate claims submitted electronically.^{10,11} Pharmacy dispensing information is usually seen as the gold standard of drug exposure information compared to self-reported information¹² or prescribing records in outpatient medical records.¹³ Drugs used during hospital stays are not recorded in this data source. Prescribing information based on physician notes may overestimate actual medication use because up to 50% of prescriptions are never filled at the pharmacy.¹⁴

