Android Methitest Testred Virilon (Methyltestosterone)	NDCs: 00187-0902-01 00115-1408-01 00187-0901-01 00115-7037-01	Clinical Pharmacology Database²⁰
Winstrol (Stanozolol)	NDCs: 0024-2253-04??	Clinical Pharmacology Database²⁰
Prophylactic use of Cinryze and Ruconest	Algorithm and code lists	Source
Cinryze prophylactic use	Cinryze is indicated for prophylaxis, but is used off-label for acute attacks. Prophylactic use will be defined as continuous refills of Cinryze averaging ≥ 1500 IU/week for ≥ 90 days.	Riedl 2018²²
Ruconest prophylactic use	Ruconest is indicated for on-demand use, but is used off-label for prophylaxis. Patients with Ruconest prophylactic use will be excluded from the cohort. Prophylaxis use will be defined as continuous refills of Ruconest averaging 50 IU/kg once weekly for 90 days.	Riedl 2018²²
every four-week	Used to determine if a dose reduction occurred.	

administration of Takhzyro	This will be measured over a 90-day follow-up period based on total dose <= 1200 mg over that period. The 1200 mg is based on three 300 mg injections plus one additional injection to account for potential variation in exact timing.	
Attack severity	Algorithm and code lists	Source
Severe	
ED visit with/without hospitalization, identified based on “Type of service” coded as inpatient or emergency room. Events identified as HAE-specific include at least one of the following diagnose (as a primary diagnosis for hospitalizations /or treatments indicative of an attack:
 
 € Codes often associated with HAE: ICD-9-CM 277.6 or ICD-10-CM D84.1 € Angioedema diagnosis: ICD-9-CM 995.1 or ICD-10-CM T78.3* € Administration of on-demand HAE treatment € Diagnosis of swelling, abdominal pain, or asphyxiation: 
 o ICD-9-CM 518.81, 518.84, 787.0*, 782.2, 789.0*, 786.02, 786.05, 786.1 o ICD-10-CM J96.0*, J96.2*, J96.9*, R06.0*, R06.1, R10.*, R11.*, R22.0*, R22.1, R19.0 	
UpToDate states severe attacks are treated in ED.²³
 
Tachdjian 2020¹
 
Zilberberg 2010²⁴
 
Longhurst & Bork, 2019

Non- severe attack	
Each dose of an on-demand therapy over two acute attack doses is considered an attack. The number of doses dispensed will be calculated from the quantity dispensed and recommended dose and
 
Any on-demand therapy administered outside an inpatient or emergency room setting will be considered a non-severe attack.
	
Utilization	Algorithm and code lists	Source

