Annex 3: Results Table Shells

Table 1: Baseline characteristics of patients with HAE

Characteristic	RWE results	Notes	Prior ICER review base case	Prior ICER review source
Mean age			39.63	Banerji et al. 2017, ³⁰ Longhurst et al. 2017, ³¹ Zuraw et al. 2010 ³²
Female, %			68.4%	Banerji et al. 2017, ³⁰ Longhurst et al. 2017, ³¹ Zuraw et al. 2010 ³²
Mean weight, females			76.4	Fryar et al. 2016 ³³
Mean weight, males			88.8	Fryar et al. 2016 ³³
List of top 10 non-HAE therapies (therapeutic class)				

Table 2: Attack rates, utilization, and costs in the six-month baseline period before initiation of prophylaxis treatment

Characteristic	RWE results	Notes	Prior ICER review base case	Prior ICER review source
ATTACK RATES AND TREATMENTS ADMINISTERED				
Mean attack rate per month (HAE-specific severe and non-severe)			3.39	Banerji et al. 2017, ³⁰ Longhurst et al. 2017, ³¹ Zuraw et al. 2010 ³²
Number of patients who are attack free in baseline period before starting prophylaxis therapy		Due to drug indications and health plan requirements, this is expected to be minimal or 0.	-	

Distribution of severe attack free months			-	
Proportion of attacks, by severity				
Severe - HAE specific			-	
Severe - All-cause			-	
Non-severe			-	
Treatment administered – Non-severe attacks				
Self			64.9%	Riedl et al, 2015 ³⁴
Home nurse			13.8%	Riedl et al, 2015 ³⁴
Outpatient			21.3%	Riedl et al, 2015 ³⁴
% of severe-HAE specific attacks resulting in hospitalization			40.9%	Zilberberg et al 2011a ³⁵
% of hospitalized patients receiving cricothyrotomy/tracheotomy			40.0%	Bork et al ³⁶
% of cricothyrotomy/tracheotomy patients who receive artificial respiration			40.0%	Bork et al ³⁶
% of hospitalized patients who are intubated			60.0%	Bork et al ³⁶
% of intubated who receive artificial respiration			26.7%	Bork et al ³⁶
% of attacks treated with these on-demand drugs				Assumption in model
Berinert			25%	
Kalbitor			25%	

Firazyr			25%	
Ruconest			25%	
BASELINE HAE-SPECIFIC COST OUTCOMES				
Costs per home nurse			\$179	Graham et al 2017 ³⁷
Costs per physician office visit			\$266	Graham et al 2017 ³⁷
Costs per ED visit			\$1,796	Zilberberg et al 2011a and 2011b ^{35,38}
Costs per hospitalization			\$5,782	Zilberberg et al 2011a and 2011b ^{35,38}
BASELINE HAE-SPECIFIC UTILIZATION OUTCOMES				
Average number of home visits			-	
Average number physician office visits			-	
Average number of ED visits			-	
Average number of hospitalizations			-	

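### An HAE-specific severe attack needs diagnosis and drug in section 5.2.1.4 but either one in Annex 2, and section 5.2.1.8 counts hospitalised patients where Table 2 needs hospitalised attacks

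*Protocol*

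**What the plan says.** Section 5.2.1.4 plans two severe definitions on purpose: "severe attack will be defined in two ways: broadly as all-cause ED visits with or without hospitalization and more specifically as HAE ED visits". It describes the HAE-specific one as an "ED visit with or without hospitalization that includes diagnoses and drugs indicative of an attack" and points to Annex 2. Section 5.2 also sends the reader to Annex 2 for every variable definition.

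Annex 2 identifies severe events by a type of service "coded as inpatient or emergency room" and then states: "Events identified as HAE-specific include at least one of the following diagnose (as a primary diagnosis for hospitalizations /or treatments indicative of an attack". The list that follows holds HAE-associated codes, angioedema codes, on-demand treatment, and symptom codes. Treatment is one item among several.

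On drug capture, section 5.3.1.2 says: "Drugs used during hospital stays are not recorded in this data source".

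On admissions, section 5.2.1.8 says: "For those patients with severe attacks, defined by inpatient hospitalization or ED visit, we will calculate the percentage of patients hospitalized". The matching research question in section 4 is also put per patient. Table 2 in Annex 3 asks instead for the percentage "of severe-HAE specific attacks resulting in hospitalization", with a prior base case of 40.9%.

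**The concern.** Two things do not line up. First, *and* in the main text and *or* in the annex select different events for the HAE-specific severe count. That count is part of the primary attack rate: the Table 2 rate row combines HAE-specific severe and non-severe attacks. The difference is not neutral, because a rule that needs a drug record works worst where drugs are not recorded, namely in admitted patients.

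Second, a share of patients and a share of attacks are different quantities, and only the second fits the Table 2 row. Section 3 says the results will supply updated inputs to the cost-effectiveness model, so the count and the hospitalised share should each have one reading. The sensitivity analyses in section 5.4.1.4 vary only the five-day window and the two on-hand doses, so they would not reveal either problem.

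**Working it through.** The protocol gives no figure that can be reproduced here. The 40.9% is a prior input from an outside source and serves below only as a working value. All other inputs are assumptions.

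**1. The texts side by side**

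| Element | Section 5.2.1.4 | Annex 2 | Section 5.2.1.8 | Table 2 |
|---|---|---|---|---|
| Diagnosis and drug | both | at least one | not stated | HAE-specific |
| Setting | ED visit, admitted or not | inpatient or ED type of service | inpatient or ED | not stated |
| Unit of hospitalised share | – | – | patient | attack |

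The five-day rule in section 5.2.1.4 also calls an attack severe when an on-demand administration falls close to an ED visit or admission, with no diagnosis needed. That fits *or* better than *and*.

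**2. *And* versus *or*: number of events**

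Let D and T be the shares of ED or inpatient events with a listed diagnosis and with a recorded treatment. If the two are independent, *and* counts D×T and *or* counts D + T − D×T.

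| D, T (assumed) | *and* | *or* | ratio |
|---|---|---|---|
| 0.8, 0.6 | 0.48 | 0.92 | 1.9 |
| 0.7, 0.5 | 0.35 | 0.85 | 2.4 |
| 0.6, 0.3 | 0.18 | 0.72 | 4.0 |
| 0.4, 0.2 | 0.08 | 0.52 | 6.5 |

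*And* can never count more events than *or*. The size of the gap depends wholly on D and T, which the documents do not give.

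**3. *And* combined with missing inpatient drugs: the hospitalised share**

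Let p = 0.409 be the true share of severe attacks admitted, and r the chance of a drug record for an admitted attack relative to an ED-only one. The observed share is p·r / (p·r + 1 − p).

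- r = 0: 0%
- r = 0.25: 0.10225 / 0.69325 = 14.7%
- r = 0.5: 0.2045 / 0.7955 = 25.7%
- r = 0.75: 0.30675 / 0.89775 = 34.2%
- r = 1: 40.9%

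The share falls whenever r is below 1, which is what section 5.3.1.2 leads one to expect. The value of r is unknown.

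**4. Per patient versus per attack**

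With k independent severe attacks per patient, the share of patients ever admitted is 1 − (1 − 0.409)^k:

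- k = 1: 40.9%
- k = 2: 1 − 0.591² = 65.1%
- k = 3: 1 − 0.591³ = 79.4%
- k = 4: 1 − 0.591⁴ = 87.8%

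If counts vary between patients as a zero-truncated Poisson, the share is (1 − e^(−0.409λ)) / (1 − e^(−λ)):

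- λ = 0.5: 47.0%
- λ = 1: 53.1%
- λ = 2: 64.6%
- λ = 3: 74.4%

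Clustering of admissions in the same patients would narrow the gap.

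**The case against.** The best defence is that Annex 2 governs. Both section 5.2 and the sentence in section 5.2.1.4 point to it, so *and* may be a loose summary of a list holding both diagnoses and drugs. That makes *or* the likely intention and lowers the seriousness. It does not settle the matter: no text says the annex prevails, its own sentence has an unclosed bracket and a stray slash, and the two places also differ on setting. It is also fair that a patient admitted through the ED may have a drug claim from the ED, so the loss of admitted attacks need not be complete.

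Four stronger readings are tempting and are not supported.

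- A reader might infer three rival definitions of a severe attack. The all-cause and HAE-specific definitions are planned, and section 5.4.1.1 and Table 2 report them separately. Section 5.2.1.8 may intend either; its fault is that it does not say which.
- A reader might infer that the severe rate fails to match a model input. Table 2 has no prior value in its severity rows. Its only attack-rate base case is the combined 3.39 per month, and that row already names HAE-specific severe attacks. The severe rate is left undetermined, not mismatched.
- A reader might infer a cost error of 28% to 45%. The arithmetic is right if the two Table 2 prices are alternatives: 0.409 × $5,782 + 0.591 × $1,796 = $3,426, against $4,390 at 65.1% and $4,959 at 79.4%. But it needs every patient to have two or three severe attacks, and the patient percentage to be entered in a row correctly labelled per attack. The protocol plans no such substitution.
- A reader might infer that counting symptom-only codes is an error. The choice rests on expert input and literature, the cohort consists of initiators of HAE-specific drugs, admissions need the code as primary diagnosis, and section 5.4.1.5 discloses that no validated algorithm exists. Criteria for using attack estimates in the model are referred to a separate Model Analysis Plan that is not shown.

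**Conclusion.** The concern holds in two limited parts, and both should be fixed.

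The contradiction between section 5.2.1.4 and Annex 2 is real and touches a primary outcome. The *and* rule would count no more severe attacks than *or*, and probably fewer. Given the missing inpatient drug records, it would bias the hospitalised share downward. The direction rests on the documents; the size cannot be derived from them, and the ranges shown only illustrate assumed inputs.

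The per-patient share in section 5.2.1.8 is a different quantity from the Table 2 row and coincides with it only at one severe attack per patient. With independent attacks the gap is 40.9% against about 65% at two attacks each, or against 47% to 74% under the Poisson counts. No severe-attack count is given, so the actual gap is unknown.

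This is a should-fix: Annex 2 and Table 2 already suggest the intended answers, but the text as it stands permits others.

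**What to change.** - In section 5.2.1.4, replace *diagnoses and drugs* with *diagnoses or on-demand drugs*, and align the setting (ED, inpatient or both) with Annex 2, so that one identical rule stands in both places. Repair the unclosed bracket in Annex 2 at the same time.
- Do not switch to a diagnosis-only rule for admissions. It would conflict with Annex 2 and with the five-day rule.
- In section 5.2.1.8, name the HAE-specific definition and compute admissions per HAE-specific severe attack, as Table 2 requires. Report the percentage of patients hospitalised as a separate supplementary figure, which still answers the research question in section 4.
- Optional: one extra row in Table 2 counting HAE-specific severe attacks without symptom-only codes.

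The cost is a few sentences and one supplementary row in Table 2. No new data are needed.

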Annex 1: HAE drugs

Generic	Brand (Administration)	Acute Attack Dose	Long-Term Prophylaxis Dose	How Supplied
C1 Inhibitor, Human (plasma derived C1 inhibitor [pdC1INH])	Cinryze* (IV)	Adults† 1,000 units once. Additional 1,000 units IV if no improvement 60 minutes after first dose. (not studied in children)	Adults & Children ≥12 years 1,000 units every 3-4 days Max Dose: 2,500 units or 100 units/kg every 3 days Children (6-11 years) 500 units every 3-4 days Max Dose: 1,000 units every 3 days Short-Term Prophylaxis† (before a procedure) 20 units/kg or 1,000 units immediately prior to procedure	Cinryze 500 units Powder Vial Reconstitute with 5mL SWFI Concentration: 100 units/mL
	Haegarda* (SC)		Adults & Children ≥6 years 60 IU/kg twice weekly (every 3-4 days)	Haegarda 2000 IU Powder Vial Reconstitute with 4mL SWFI Concentration: 500 IU/mL Haegarda 3000 IU Powder Vial Reconstitute with 6mL SWFI Concentration: 500 IU/mL
	Berinert* (IV)	Adults & Children ≥6 year 20 IU/kg once		Berinert 500 IU Power Vial Reconstitute with 10mL SWFI Concentration: 50 IU/mL

Generic	Brand (Administration)	Acute Attack Dose	Long-Term Prophylaxis Dose	How Supplied
Lanadelumab	Takhzyro* (SC)		Adults & Children ≥12 years 300mg every 2 weeks. After 6 months, reduce to every 4-week dosing if patient well-controlled.	Takhzyro 300mg/2mL Solution Vial Concentration: 150mg/mL
C1 Esterase Inhibitor, Recombinant (recombinant human C1 inhibitor [rhC1INH])	Ruconest* (IV)	Adults & Children ≥13 years (non-laryngeal attacks) 50 IU/kg/dose Max Dose: 4,200 IU/dose; 8400 IU per 24 hours	Adults & Children ≥13 years† 50 IU/kg/dose once or twice weekly Max Dose: 4,200 IU/dose once or twice weekly Short-Term Prophylaxis† (before a procedure) 50 IU/kg or 1,000 units immediately prior to procedure	Ruconest 2100 IU Powder Vial Reconstitute with 14mL SWFI Concentration: 150 IU/mL
Ecallantide	Kalbitor* (SC)	Adults & Children ≥12 years 30mg once (administered as three injections of 10mg) Max Dose: 60mg in 24 hours		Kalbitor 10mg/mL Vial Solution for Injection (3 vials per package)
Icatibant	Firazyr (SC)	Adults 30mg once. Repeat administrations in 6-hour intervals. Max Dose: 90mg in 24 hours (EU Pediatric Dosing Weight Based)		Firazyr 30mg/3mL Solution Vial Icatibant 30mg/3mL Solution Prefilled Syringe
Berotrastat	Orladeyo* (Oral)		Adults & Children ≥12 years 150 mg once daily. Adjustment: 110mg once daily for hepatic impairment or GI reactions.	Orladeyo 110mg Capsule Orladeyo 150mg Capsule

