Annex 2: Variable definitions and code lists

Treatment - Brand Name (Generic)	J Codes and NDCs	Source
Takhzyro (lanadelumab)	J0593 Injection, lanadelumab-flyo, 1 mg (code may be used for Medicare when drug administered under direct supervision of a physician, not for use when drug is self-administered) NDCs: 47783-0644-01	Clinical Pharmacology Database²⁰ and HCPCS²¹
Haegarda (C1 Inhibitor)	J0599 - Injection, HAEGARDA, 10 units (effective Jan 1, 2019) NDCs: 63833-0828-02 63833-0829-02	Clinical Pharmacology Database²⁰ and HCPCS²¹
Cinryze (C1 Inhibitor)	J0598 - Injection, C1 esterase inhibitor (human), 10 units NDCs: 42227-0081-01 42227-0081-05	Clinical Pharmacology Database²⁰ and HCPCS²¹
Ruconest (C1 Esterase Inhibitor, Recombinant)	J0596 - Ruconest, 10 units NDCs: 68012-0350-01 68012-0350-02 71274-0350-01 71274-0350-02	Clinical Pharmacology Database²⁰ and HCPCS²¹
Kalbitor (ecallantide)	J1290 - Injection, ecallantide, 1 mg NDCs: 47783-0101-01	Clinical Pharmacology Database²⁰ and HCPCS²¹
Berinert (C1 Inhibitor)	J0597 - Injection, C1 Esterase Inhibitor (Human), BERINERT, 10 units NDCs: 63833-0825-02	Clinical Pharmacology Database²⁰ and HCPCS²¹
Firazyr (icatibant)	J1744 - Injection, icatibant, 1 mg NDCs: 00093-3066-19	Clinical Pharmacology Database²⁰

	00093-3066-34 00093-3066-93 24201-0207-01 24201-0207-03 54092-0135-01 54092-0135-02 54092-0702-02 54092-0702-03 60505-6214-01 63323-0574-01 63323-0574-86 63323-0574-93 69097-0664-34 69097-0664-68	and HCPCS²¹
Orladeyo (berotralstat)	Newly approved drug (December 2020) and not available in the analysis data set which runs through March 31st 2020.	
Danazol (Danocrine)	NDCs: 00527-1368-01 00527-1369-01 00527-1369-06 00527-1392-01 00555-0633-02 00555-0634-02 00555-0635-02 00555-0635-09 42291-0243-01	Clinical Pharmacology Database²⁰
Cykokapron Lysteda (Tranexamic Acid)	NDCs: 00591-3720-30 55566-2100-01 55566-2110-02 60505-3638-01 60505-3638-03 66993-0090-30 66993-0121-30 69918-0301-30	Clinical Pharmacology Database²⁰
Amicar (Aminocaproic Acid)	NDCs: 17478-0447-08 17478-0768-30 17478-0769-30 49411-0050-30 49411-0051-30 49411-0052-08	Clinical Pharmacology Database²⁰

	52817-0815-08 60219-1637-03 60687-0505-25 62559-0225-30 66689-0330-08 69238-1596-08 69680-0115-30 69680-0116-30 72205-0049-30	
Oxandrin (Oxandrolone)	NDCs: 49884-0301-01 00185-0271-01 49884-0302-02 00185-0272-60	Clinical Pharmacology Database²⁰

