cricothyrotomy/ tracheotomy	emergency tracheotomy (31603) and an emergency cricothyrotomy (31605)	
Dillon 2013²⁵
 
Esposito²⁶

intubation	The appearance of any of the following encounters CPT - 31500 ICD10 - 09HN7BZ, 0DH57BZ, 0DH58BZ, 0WHQ73Z, 0WHQ7YZ, 09HN8BZ, 0B21XEZ, 0BH13EZ, 0BH17EZ, 0BH18EZ, 0CHY7BZ, 0CHY8BZ ICD9 - 96.04, 96.7x, 96, 96.0,96.5	Pandya 2019²⁷ Singh 2020²⁸ De novo code look up
artificial respiration	The appearance of any of the following encounters Invasive mechanical ventilation: CPT - 94002, 94003, 94004, 94005, E0472, K0534 ICD10 - 5A1935Z, 5A1945Z, 5A1955Z noninvasive ventilation: CPT - 94660, A7027, A7034, A7044, E0452, E0470, E0471, E0601, K0183, K0193, K0194, K0532, K0533 ICD10 - 5A09459, 5A09557, 5A09357, 5A09358, 5A09359, 5A0935B, 5A09457, 5A09458, 5A0945B, 5A09558, 5A09559, 5A0955B ICD9 - 93.90 ventilation NOS: CPT- 94656, 94657 ICD10 - 5A0920Z, 5A0945Z, 5A0955Z, 5A19054, 5A0935Z, 5A09358, 5A0935B,	Pandya 2019²⁷ Singh 2020²⁸ Rosenthal 2020²⁹ De novo code look up
Costs	Algorithm and code lists	Source
Home nurse treatment	Standard cost amount for medical service claims with an on-demand drug administration where the place of service is ‘home’	
Physician office visit	Standard cost amount for medical service claims with an on-demand drug administration where the place of service is ‘office’	
ED visit	Standard cost amount for medical service claims where the type of service is coded as ‘emergency room, professional or facility’	
Hospitalization	Standard cost amount for medical service claims where the type of service is coded as ‘acute inpatient facility’	

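### A non-ED, non-inpatient medical claim for an on-demand drug counts as one attack whatever units are billed, while dispensed drug counts as doses above two, so the attack count can depend on billing route

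*Protocol*

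**What the plan says.** The protocol counts non-severe attacks in two ways.

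- **Treated by a professional.** Section 5.2.1.4: "An attack treated by a healthcare professional will be defined as a medical service claim for an on-demand therapy", for settings other than inpatient and ED. The Annex 2 row on non-severe attacks agrees: "Any on-demand therapy administered outside an inpatient or emergency room setting will be considered a non-severe attack". Neither sentence refers to quantity.
- **Self-administered.** Section 5.2.1.4: "we will estimate the number of attacks treated by calculating the number of doses dispensed based on dispensed quantity and approved dosages", and the plan then takes "any doses dispensed over the two on-hand dosages of on-demand therapy as evidence of an attack". Annex 2 agrees: "Each dose of an on-demand therapy over two acute attack doses is considered an attack".

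Annex 2 identifies on-demand drugs by both NDC and J-code. The J-codes are billed per 1 mg (icatibant, ecallantide) or per 10 units (Berinert, Ruconest); for example, "J1744 - Injection, icatibant, 1 mg". The home-nurse and office cost rows of Annex 2 select claims by setting: "Standard cost amount for medical service claims with an on-demand drug administration where the place of service is" home or office respectively.

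**The concern.** The unit of count differs by route: a claim on one side, a dose above two on the other. No rule tells a medical claim for one administration from a medical claim for a supply to be kept at home. A multi-dose supply billed by J-code with place of service home would be counted once and classed as home-nurse treatment, although the billed units show that it holds several doses.

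The outputs affected are primary ones. The non-severe count enters the baseline attack rate (Section 5.4.1.1) and the self / home-nurse / outpatient split in Annex 3, Table 2. Section 4 itself warns that small changes in attack frequency could alter the cost-effectiveness results substantially.

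**Working it through.** The protocol gives no figure of its own to reproduce here, so the check applies its two rules to the same supply.

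**Inputs**
- Icatibant acute dose (Annex 1): "30mg once. Repeat administrations in 6-hour intervals".
- J1744 unit (Annex 2): 1 mg. One dose is therefore 30 mg / 1 mg = 30 billed units.
- On-hand deduction (Section 5.2.1.4): two doses. One sensitivity analysis drops it, for self-administration only (Section 5.4.1.4).

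**Formulas for one supply of k doses**
- Medical claim: 1.
- Dispensed, main analysis: max(0, k - 2).
- Dispensed, sensitivity analysis: k.

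| Doses k | J1744 units (30k) | Medical claim | Dispensed, main | Dispensed, no deduction |
|---|---|---|---|---|
| 1 | 30 | 1 | 0 | 1 |
| 2 | 60 | 1 | 0 | 2 |
| 3 | 90 | 1 | 1 | 3 |
| 4 | 120 | 1 | 2 | 4 |
| 6 | 180 | 1 | 4 | 6 |
| 12 | 360 | 1 | 10 | 12 |

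For a single supply the main-analysis routes agree only at three doses.

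**Repeated supply.** Take six monthly supplies of three doses over the six-month baseline. Billed medically, the rate is 6/6 = 1.00 attack per month. Dispensed, it is (18 - 2)/6 = 2.67 if two doses are deducted once, 6 x (3 - 2)/6 = 1.00 if they are deducted at every fill, and 18/6 = 3.00 with no deduction. The gap therefore also depends on how the deduction is applied.

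**Does another rule repair this?** The five-day rule merges separate claims; it cannot split one claim into doses. The sensitivity analyses in Section 5.4.1.4 vary the merging window and the two-dose deduction, not the units on a medical claim.

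**Possible size.** Let q be the share of all non-severe doses that are medically billed supply, in claims of k doses. Of N doses, qN produce only qN/k counts, so the loss as a share of all non-severe doses is q(1 - 1/k). This ignores the deduction and treats each dose as one attack.
- q = 10%, k = 4: 0.10 x 0.75 = 7.5%.
- q = 30%, k = 4: 0.30 x 0.75 = 22.5%.
- Within the medically billed part alone, the loss at k = 4 is 75%, whatever q is.

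The values of q and k are assumptions. For scale only, take the prior base case of 3.39 attacks per month (Table 2), suppose every attack is non-severe and all others are counted correctly, and let a share s be treated from k-dose medical claims. The counted rate is 3.39 x (1 - s + s/k).
- s = 5%: 3.31 (k = 2) to 3.25 (k = 6).
- s = 13.8%, the prior home-nurse share borrowed as a marker: 3.16 (k = 2) to 3.00 (k = 6).

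**The case against.** **The premise is not documented.** The protocol never says that multi-dose on-demand supply is billed by J-code to the home. Its one note on J-code use concerns Takhzyro, a prophylactic drug, and ties that code to supervised administration. A reader might infer that such supply is common; the text does not support that. This stands, so the size can only be a range.

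**The rule is about administration, not billing.** Annex 2 speaks of drug administered, and the protocol never calls the other route a pharmacy claim. For a true single administration, one claim for one attack is reasonable. That also stands, but Section 5.2.1.4 makes the presence of a medical claim the definition of an administration and attaches no test.

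**A protocol may leave claim handling to the analysis plan.** That would answer a missing detail. Here the protocol fixes the counting unit for each route, and the two units differ.

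**The direction is not uniform.** A reader might infer that the attack rate is simply biased down. The table does not support this: for one or two doses the medical route counts more. Some multi-dose claims are also rightly one attack, since Annex 1 allows icatibant up to 90 mg in 24 hours, which is three doses.

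**Drug cost is excluded.** A reader might infer that supply claims would inflate the home-nurse cost. Section 5.2.1.5 removes on-demand drug costs from attack costs and Section 5.2.1.6 removes HAE drug costs from HAE-related baseline costs. The Annex 2 cost rows do not repeat this, but those sections govern. What remains is a risk of dilution by episodes with little or no service cost.

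**The absence of a validated algorithm is disclosed.** Sections 5.2.1.4 and 5.4.1.5 say so. That is a general caveat and does not deal with a difference between routes that the billed units could reveal.

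**Conclusion.** The point holds in a conditional form. On the protocol's wording, identical supply can yield different attack counts according to how it is billed, and no rule or sensitivity analysis corrects this. Whether it matters in these data depends on how often multi-dose supply appears on medical claims outside the ED and inpatient settings, which only a tabulation can show. If it is rare, the effect is negligible. If q is 10-30% at four doses per claim, the 7.5-22.5% shortfall is a share of all non-severe doses, under the two simplifications stated with the formula. The net direction in the main analysis turns on supply size and on how the deduction is applied. The home-nurse share would be overstated by any supply claim placed there, and the home-nurse mean cost would more likely fall than rise. Because the primary rate and the treatment-setting split are exposed and the check is cheap, the rule should be changed.

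**What to change.** 1. Before counting, tabulate billed units per non-ED, non-inpatient medical claim, by product and place of service, and convert them to doses using Annex 1.
2. Add a rule to Annex 2: a claim is a single professional administration only if its units are compatible with treating one attack. Where Annex 1 gives a 24-hour maximum, that sets the limit: icatibant 90 mg = 90 units, ecallantide 60 mg = 60 units, Ruconest 8,400 IU / 10 = 840 units. Berinert has none and needs a stated weight assumption; at the Table 1 prior-review mean weights, read as kg, one dose is 20 x 76.4 / 10 = 152.8 or 20 x 88.8 / 10 = 177.6 units. Off-label acute Cinryze needs its own stated rule if it is counted. These limits serve only to classify claims and say nothing about treatment.
3. Count larger claims under the dispensed-dose rule, with the on-hand deduction applied as for other dispensed drug, and remove them from the home-nurse and office shares and costs.
4. Report the attack rate with and without this reclassification.

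The cost is one table, one Annex 2 rule and one extra rate. The downside is that some large true administrations will be reclassified as supply, and supplies of two or three doses will still count as one administration. For a single supply that residual gap is small in the main analysis, but it can grow with repeated supplies.
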